#### 8.2 Adverse Events

An AE is defined as any untoward medical occurrence in a clinical investigation participant administered a pharmaceutical product, which does not necessarily have a causal relationship with this treatment. An AE can therefore be any unfavorable and/or unintended sign (including an abnormal laboratory finding), symptom, or disease temporally associated with the use of an investigational medicinal product, whether or not related to the investigational medicinal product. All AEs, including observed or volunteered problems, complaints, or symptoms, are to be recorded on the appropriate eCRF.

AEs, which include clinical laboratory test variables, will be monitored and documented from the time of signing of informed consent at Screening (Visit 1) until the EOS Visit (35 days after the EOT Visit). Participants should be instructed to report any AE that they experience to the Investigator, whether or not they think the event is due to study treatment. Beginning at the time of signing of informed consent, Investigators should make an assessment for AEs at each visit and record the event on the appropriate AE eCRF.

Wherever possible, a specific disease or syndrome rather than individual associated signs and symptoms should be identified by the Investigator and recorded on the eCRF. However, if an observed or reported sign or symptom is not considered a component of a specific disease or syndrome by the Investigator, it should be recorded as a separate AE on the AE eCRF. Additionally, the condition that led to a medical or surgical procedure (eg, surgery, endoscopy, tooth extraction, or transfusion) should be recorded as an AE, not the procedure itself.

Any medical condition already present at Screening (Visit 1) should be recorded as medical history and not be reported as an AE unless the medical condition or signs or symptoms present at Baseline changes in severity, frequency, or seriousness at any time during the study. In this case, it should be reported as an AE.

Clinically significant abnormal laboratory or other examination (eg, ECG) findings that are detected during the study or are present at Screening (Visit 1) and significantly worsen during the

study should be reported as AEs, as described below. The Investigator will exercise his/her medical and scientific judgment in deciding whether an abnormal laboratory finding or other abnormal assessment is clinically significant. Clinically significant abnormal laboratory values occurring during the clinical study will be followed until repeat tests return to normal, stabilize, or are no longer clinically significant. Abnormal test results that are determined to be an error should not be reported as an AE.

Laboratory abnormalities or other abnormal clinical findings (eg, ECG abnormalities) should be reported as an AE if any of the following are applicable:

- If an intervention is required as a result of the abnormality;
- If action taken with the study drug is required as a result of the abnormality; or
- Based on the clinical judgment of the Investigator.

## 8.2.1 Adverse (Drug) Reaction

All noxious and unintended responses to a medicinal product related to any dose should be considered adverse drug reactions. "Responses" to a medicinal product means that a causal relationship between a medicinal product and an AE is at least a reasonable possibility, ie, the relationship cannot be ruled out.

## 8.2.2 Unexpected Adverse Drug Reaction

An unexpected adverse drug reaction is defined as an adverse reaction, the nature or severity of which is not consistent with the applicable product information.

## 8.2.3 Assessment of AEs by the Investigator

The Investigator will assess the severity (intensity) of each AE as mild, moderate, or severe, and will also categorize each AE as to its potential relationship to study drug using the categories of yes or no.

#### Assessment of severity

Mild – An event that is easily tolerated and generally not interfering with normal daily activities.

Moderate – An event that is sufficiently discomforting to interfere with normal daily activities.

Severe – An event that is incapacitating with inability to work or perform normal daily activities.

#### Causality assessment

The relationship of an AE to the administration of the study drug is to be assessed according to the following definitions:

No (not related or unlikely to be related) – The time course between the administration of study drug and the occurrence or worsening of the AE is not consistent with a causal relationship and another cause (concomitant drugs, therapies, complications, etc) is suspected.

Yes (possibly, probably, or definitely related) – The time course between the administration of study drug and the occurrence or worsening of the AE is consistent with a causal relationship and no other cause (concomitant drugs, therapies, complications, etc) can be identified.

The definition implies a reasonable possibility of a causal relationship between the event and the study drug. This means that there are facts (evidence) or arguments to suggest a causal relationship.

The following factors should also be considered:

• The temporal sequence from study drug administration-

The event should occur after the study drug is given. The length of time from study drug exposure to event should be evaluated in the clinical context of the event.

• Underlying, concomitant, intercurrent diseases-

Each report should be evaluated in the context of the natural history and course of the disease being treated and any other disease the participant may have.

• Concomitant drug-

The other drugs the participant is taking or the treatment the participant receives should be examined to determine whether any of them might be recognized to cause the event in question.

• Known response pattern for this class of study drug-

Clinical and/or preclinical data may indicate whether a particular response is likely to be a class effect.

Exposure to physical and/or mental stresses-

The exposure to stress might induce adverse changes in the recipient and provide a logical and better explanation for the event.

• The pharmacology and PK of the study drug-

The known pharmacologic properties (absorption, distribution, metabolism, and excretion) of the study drug should be considered.

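### The yes/no causality definitions leave some adverse events in neither category and are narrower than the protocol's own reasonable-possibility standard

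*Protocol*

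**What the plan says.** Protocol 8.2.3 tells the investigator to "categorize each AE as to its potential relationship to study drug using the categories of yes or no". There is no third answer.

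The Causality assessment text in that section then defines the two answers:

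- *No*: the time course "is not consistent with a causal relationship and another cause (concomitant drugs, therapies, complications, etc) is suspected".
- *Yes*: the time course fits causation by study drug, and "no other cause (concomitant drugs, therapies, complications, etc) can be identified".

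Three other statements bear on what *Yes* is meant to cover:

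- The label on the *Yes* category reads "Yes (possibly, probably, or definitely related".
- Directly after the definitions, the protocol says that they imply a reasonable possibility of causation, and explains: "This means that there are facts (evidence) or arguments to suggest a causal relationship". A list of factors to weigh follows, including underlying disease, concomitant drugs, class pattern and pharmacology.
- Protocol 8.2.1 describes an adverse drug reaction as a response for which "a causal relationship between a medicinal product and an AE is at least a reasonable possibility, ie, the relationship cannot be ruled out".

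The SAP uses the answer in 3.5.1 (study-drug-related TEAEs, overall and by maximum severity, and related TESAEs) and in 3.5.2 (new-onset diabetes and macular degeneration by relationship). SAP 3.1.8 does not impute missing safety data.

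**The concern.** Each definition joins two conditions with *and*, so the pair does not divide all events between them. The event that matters most has plausible timing and another candidate cause. It is a realistic case here: participants have HeFH and/or ASCVD and are on maximally tolerated lipid-modifying therapy, and the Synopsis requires at least 70% to be on high-intensity statins. The protocol asks the investigator to look for concomitant drugs and underlying disease that could explain the event. On the literal wording, an investigator who identifies one can no longer answer *Yes*, even where 8.2.1 would still treat the event as a reaction.

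At stake is how events are classified, and whether that is consistent across approximately 180 sites. Two investigators could code the same event differently, one following the clause and the other the explanatory sentence.

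**Working it through.** No figure is involved, so the check is a reading of the text. Cross timing with the presence of another cause and apply the two definitions as written.

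| Timing | Other cause | Literal category |
|---|---|---|
| Consistent | None identifiable | *Yes* |
| Consistent | Identifiable | Neither |
| Not consistent | Suspected | *No* |
| Not consistent | None | Neither |

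Two of the four combinations are unassigned.

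**Second row against the rest of the protocol.** The label admits events that are only possibly related. The explanatory sentence asks for evidence or argument suggesting causation, which can coexist with a rival explanation. Section 8.2.1 includes an event where "the relationship cannot be ruled out". All three can be satisfied by a second-row event, but the *Yes* definition excludes it. The literal *Yes* set is therefore narrower than the protocol's own standard.

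**Direction for the second row.** If such an event is marked *No*, it is absent from the related counts. If it is left blank, SAP 3.1.8 supplies no value and it is not counted as related either. For these events, literal use can only lower the related counts.

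**Fourth row.** The *No* label includes events unlikely to be related, so this row has a natural home there. It is a drafting gap with little practical effect.

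**Where the answer is used.**

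- SAP 3.5.1 and 3.5.2: the related-event tables and the relationship summaries named above.
- Protocol 5.4: the sponsor or designee unblinds reports of SAEs that are unexpected and considered related.
- Protocol 8.6: expedited reporting of suspected unexpected serious adverse reactions.
- Protocol 8.4: after the reporting window, the duty to report an SAE turns on the investigator considering it related.

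**Where it is not used.**

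- Protocol 8.2: all AEs are recorded.
- Protocol 8.4: SAEs up to 35 days after the last dose are reported whatever the investigator's view of relatedness.
- Protocol 8.2.5, 8.6.1 and 9.2.5: the DSMB reviews unblinded safety data, including events of special interest, about every 6 months.
- SAP 3.5.1: all TEAEs, TESAEs, discontinuations and deaths are also tabulated irrespective of relationship.

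**The case against.** The best defence is that the definitions should be read with the text around them. The reasonable-possibility sentence follows at once, the listed factors would have little purpose if any rival cause automatically ruled out *Yes*, and the label itself includes possible relationships. The wording is also less severe than it first looks: *No* needs only a suspected alternative, whereas *Yes* is barred only by one that can be identified. A statin that has been stable for at least 8 weeks before Screening (Protocol 5.6.2) is not automatically the identified cause of a new event. In practice each AE must receive a yes or no, and missing data are queried (Protocol 10.1.5).

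Much of this stands. It shows that a careful investigator can reach the intended answer, and that the intended standard is already in the protocol. It does not remove the conflict: the operative definition still says something different from its label, its explanation and 8.2.1, and the reader must choose which to follow.

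A reader might go further and infer that related events are in fact under-reported, that almost nothing would be rated related in this population, or that reporting of unexpected serious reactions is suppressed. The documents do not support these readings. They give no share of AEs with an identifiable alternative cause and no information on how sites apply the clause. Expedited reporting is a sponsor or designee duty. Section 5.4 does not limit the judgement of relatedness to the investigator's answer, and in-window SAEs are due within 24 hours regardless of that answer. An effect on expedited reporting is possible but not shown.

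**Conclusion.** The point holds as a defect of definition. The two categories are not exhaustive, and the literal *Yes* conflicts with the protocol's own standard. Investigators who apply the clause literally may under-classify events as related, and coding may differ between sites.

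The conclusion assumes that at least some investigators follow the definition rather than the explanatory sentence or 8.2.1. The size cannot be computed from the documents. In-window, the consequence is one of classification, not capture. Only for SAEs after the reporting window could it affect whether an event is reported at all. The SAP tables concerned are descriptive, with no inference on safety endpoints (SAP 3.5), and no efficacy or power figure is affected. The rewording is worth making because it is cheap and the field feeds several safety outputs.

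**What to change.** Reconcile the Causality assessment text in Protocol 8.2.3 with 8.2.1:

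- Define *Yes* as a reasonable possibility that study drug caused or contributed to the event, even if other causes are possible.
- Define *No* as no reasonable possibility.
- Delete the condition that no other cause can be identified.
- Keep the listed factors as considerations to be weighed.

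As a companion change, SAP 3.5.1 could state how an event with a missing relationship is counted.

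The cost is wording in the protocol and the eCRF guidance. Somewhat more events are likely to be rated related. They would be assessed under the same blinded rule in both arms, but the added numbers need not be equal, given 2:1 allocation and any true drug effect. If the wording changes while events are still being coded, the date of the change should be recorded, because relatedness before and after it will rest on different definitions.

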#### 8.2.4 CV Events

By the design of this study, CV events will be captured as exploratory endpoints (see Section 7); these events will be reviewed and adjudicated by an independent CEC and reported in the appropriate clinical endpoint eCRF. In addition, these events are subject to normal AE/SAE reporting procedures.

#### 8.2.5 Events of Special Interest

ESIs will be monitored over time by the independent DSMB on a bi-annual basis (ie, approximately every 6 months), regardless of whether these events were reported as AEs. Any events that qualify as an AE or SAE will be reported accordingly (see Sections 8.2, 8.3, and 8.4).

ESIs will include the following hepatic abnormalities, muscle-related abnormalities, new-onset diabetes mellitus (NODM) and/or hyperglycemia, renal abnormalities, changes to antihypertensive medication(s) due to changes in blood pressure, and ophthalmic events (ie, macular degeneration), described as follows:

- AST or ALT > 3 × ULN;
- Total bilirubin >2 × ULN;

- CK >5 × ULN;
- NODM or worsening of glycemic control;

Note: NODM is defined by 1 or more of the following criteria, based upon information from AE, medication, and laboratory data:

- o AE indicating new type 1 or type 2 diabetes;
- o Initiation of anti-diabetes medication with confirmation of the diagnosis of diabetes by blinded external review by experts in diabetology;
- HbA1c  $\geq$ 6.5% ( $\geq$ 0.065 hemoglobin fraction); and/or
- Two consecutive values of fasting plasma glucose that are  $\ge 126$  mg/dL ( $\ge 7.0$  mmol/L).

Note: Worsening of glycemic control will be defined as an HbA1c increase from Baseline >0.5% (>0.005 hemoglobin fraction) and/or a new concomitant medication or increase in current antidiabetic therapy in a participant with a Baseline HbA1c  $\ge$ 6.5% ( $\ge$ 0.065 hemoglobin fraction).

- A >25% decrease in eGFR from Baseline or an eGFR <30 mL/min/1.73 m², calculated using the Chronic Kidney Disease Epidemiology Collaboration equation, and/or an increase in serum creatinine of ≥0.3 mg/dL (≥26.5 μmol/L) from Baseline;
- Changes to antihypertensive medication(s) due to changes in blood pressure in those participants receiving antihypertensive medication(s) treatment at Baseline; and
- Macular degeneration.

These ESIs will be monitored through review of the AE and laboratory databases.

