# 8.2.5.5 Guidelines for monitoring and management of changes to antihypertensive medication(s)

Any changes to antihypertensive medication(s) due to changes in blood pressure in those participants receiving antihypertensive medication(s) treatment at Baseline will be assessed by the Investigator, primary care physician, or other appropriate health care provider to assess for etiologies of blood pressure change, to confirm clinical safety of the participant, to assess the need for any AE or SAE reporting, and to arrange for appropriate medical follow-up.

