## 9.2.2.1 Analysis of ESIs

Liver-associated enzymes and total bilirubin will be summarized by the value and change from Baseline in the value, by treatment group and visit. In addition, the number and percent of participants with abnormal values for ALT, AST, and total bilirubin will be summarized. These summaries of participants with abnormal values will be performed overall; by normal Baseline; and by abnormal Baseline for ALT, AST, and total bilirubin individually. Hy's Law criteria (>3 × ULN for either ALT or AST, with accompanying total bilirubin >2 × ULN) will also be applied to the data. Any potential Hy's Law cases will be listed separately.

Muscle-related abnormalities will be summarized by treatment group and by Baseline eGFR category.

CK levels will be summarized by the value and change from Baseline in value, by treatment group and visit. In addition, the number and percent of participants with abnormal CK values will be summarized. These summaries of participants with abnormal CK values will be performed overall, by normal Baseline CK, and by abnormal Baseline CK. Values of CK from Baseline to EOT will be summarized by treatment group and by Baseline eGFR category.

Cases of NODM will be recorded and summarized using the appropriate system organ class. These events will be summarized by severity and relationship to study drug for each treatment group. Fasting plasma glucose and HbA1c will be monitored as specified in Appendix A.

Baseline eGFR will be summarized by treatment group for actual value and for Baseline eGFR categories. Shift tables of eGFR category from Baseline to EOT will be provided by treatment group. Shift tables of urine albumin-creatinine ratio and urine protein-creatinine ratio from Baseline to EOT will be provided by treatment group.

The number and percentage of participants receiving antihypertensive medication(s) treatment at Baseline with changes to antihypertensive medication(s) due to changes in blood pressure will be summarized by treatment group.

Cases of macular degeneration will be recorded and summarized using the appropriate system organ class. These events will be summarized by severity and relationship to study drug for each treatment group.

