bilirubin $>2 \times$ ULN) will also be applied to the data. Any potential Hy's Law cases will be listed separately.

Muscle-related abnormalities will be summarized by treatment group and by Baseline eGFR category.

Values and changes from baseline will be summarized for CK levels by visit and treatment group and visit. In addition, the number and percent of participants with abnormal CK values will be summarized. These summaries of participants with abnormal CK values will be performed overall, by normal Baseline CK, and by abnormal Baseline CK. Values of CK from Baseline to EOT will be summarized by treatment group and by Baseline eGFR category.

Cases of NODM will be recorded and summarized using the appropriate system organ class. These events will be summarized by severity and relationship to study drug for each treatment group. Fasting plasma glucose and HbA1c will be monitored as specified in [Table 1 Schedule of Procedures](#).

Baseline eGFR will be summarized by treatment group for actual value and for Baseline eGFR categories. Shift tables of eGFR category from Baseline to EOT will be provided by treatment group. Shift tables of urine albumin-creatinine ratio and urine protein-creatinine ratio from Baseline to EOT will be provided by treatment group.

Participants will be identified who had a diagnosis of hypertension in their medical history and received antihypertensive medication(s) at Baseline. If participants had an adverse event related to hypertension after Baseline (see [Appendix B](#) for preferred terms) and had any change in antihypertension medication within 30 days of the start date of the adverse event, that change in antihypertension medication will be considered as due to a change in blood pressure.

Participants will be identified who did not have a prior diagnosis of hypertension in their medical history and did not receive antihypertensive medication(s) at Baseline. If participants had an adverse event of hypertension and had initiation of antihypertension medication within 30 days of the start date of the adverse event, that initiation of an antihypertension medication will be considered as due to a change in blood pressure.

The number and percentage of participants receiving/not receiving antihypertensive medication(s) at Baseline with changes to or initiation of new antihypertensive medication(s) due to changes in blood pressure will be summarized by treatment group.

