APPENDIX B: PREFERRED TERMS FOR HYPERTENSION

Preferred Term
Accelerated hypertension
Blood pressure ambulatory increased
Blood pressure diastolic increased
Blood pressure inadequately controlled
Blood pressure increased
Blood pressure orthostatic increased
Blood pressure systolic increased
Diastolic hypertension
Essential hypertension
Hypertension
Malignant hypertension
Mean arterial pressure increased
Systolic hypertension
Blood pressure abnormal
Blood pressure ambulatory abnormal
Blood pressure diastolic abnormal
Blood pressure orthostatic abnormal
Blood pressure systolic abnormal
Labile blood pressure
Hypertensive crisis
Hypertensive emergency
Hypertensive urgency
Orthostatic hypertension

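### The antihypertensive-change ESI has no direction in the protocol, and the SAP rule for participants treated at Baseline still counts reductions, and stops that came before the AE, as responses to a blood pressure change

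*Protocol*

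**What the plan says.** Protocol 8.2.5 lists the event as "Changes to antihypertensive medication(s) due to changes in blood pressure in those participants receiving antihypertensive medication(s) treatment at Baseline". Protocol 9.2.2.1 plans a single figure per arm: "The number and percentage of participants receiving antihypertensive medication(s) treatment at Baseline with changes to antihypertensive medication(s) due to changes in blood pressure". Protocol 8.2.5.5 asks that such changes be reviewed "to assess for etiologies of blood pressure change", again without direction. In the same section 8.2.5, the medication part of the worsening-glycemia event does have a direction: it counts "a new concomitant medication or increase in current antidiabetic therapy".

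SAP 3.5.2 turns the event into a derivation with two strata.

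- **Hypertension history and treated at Baseline.** The participant counts if, after Baseline, he or she had an AE from the Appendix B list and "had any change in antihypertension medication within 30 days of the start date of the adverse event".
- **No hypertension history and untreated at Baseline.** Only initiation of an antihypertensive near a hypertension AE counts.

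The SAP then summarises by treatment group, without a split by direction. Appendix B contains terms such as "Labile blood pressure".

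**The concern.** The ESI sits alongside the ABPM substudy as a check on whether the drug raises blood pressure. A drug that does so should lead to more added or increased antihypertensives and, if anything, fewer reductions. A count that pools the two mixes a signal with its opposite.

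Time order raises a second problem. If a participant stops an antihypertensive for another reason and pressure then rises, the stop may be the cause of the AE. A rule that looks only at closeness in time scores it as the response.

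At stake is how clearly the final ESI table would show an excess of treatment escalation in the obicetrapib arm. Office and ambulatory readings do not fully replace this count, because they are taken after any change in treatment and an escalation that works lowers the later reading.

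**Working it through.** The documents give no rate, power or sample size for this ESI, so there is no figure of the plan's to reproduce. The check compares the definitions, then illustrates the size with assumed rates.

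**1. What each text counts**

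| Case | Protocol 8.2.5 / 9.2.2.1 | SAP 3.5.2 |
|---|---|---|
| Treated at Baseline, drug added for raised pressure, hypertension AE reported | counted | counted |
| Treated at Baseline, dose cut for low pressure, no hypertension AE | counted | not counted |
| Treated at Baseline, dose cut or stop within 30 days of a hypertension AE | counted if due to blood pressure | counted |
| No history, untreated at Baseline, drug started near a hypertension AE | outside the definition | counted (initiation only) |

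**2. Time order.** Suppose a drug is stopped on Day 100 for a reason unrelated to blood pressure, and a hypertension AE starts on Day 120. The gap is 120 − 100 = 20 days, within 30. The SAP sentence does not say that the change must follow the AE, so as written the stop is scored as due to a change in blood pressure that had not yet occurred.

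**3. Appendix B.** The list has 23 preferred terms. Five describe an abnormal reading (general, ambulatory, diastolic, orthostatic, systolic) and one is "Labile blood pressure". That makes 5 + 1 = 6 terms without direction; the other 23 − 6 = 17 denote raised or inadequately controlled pressure.

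**4. Size under the protocol wording (all rates assumed).** Each participant has at most one kind of change. Pooled ratio = (increases + reductions, obicetrapib) / (increases + reductions, placebo).

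| Placebo up / down | Obicetrapib up / down | Pooled rates, obicetrapib v placebo | Pooled ratio | Ratio, increases only |
|---|---|---|---|---|
| 5% / 5% | 7.5% / 2.5% | 10.0% v 10.0% | 1.00 | 1.50 |
| 5% / 3% | 7.5% / 1.5% | 9.0% v 8.0% | 1.125 | 1.50 |
| 5% / 1% | 7.5% / 0.5% | 8.0% v 6.0% | 1.33 | 1.50 |
| 8% / 5% | 10.4% / 3.5% | 13.9% v 13.0% | 1.07 | 1.30 |

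Cancellation is complete in the first row and partial in the others. It shrinks as reductions become rarer.

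**5. Size under the SAP rule.** Take the first row and let f be the share of reductions that fall within 30 days of an Appendix B AE. All increases are assumed to be counted. Ratio = (7.5 + 2.5f) / (5 + 5f).

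- f = 0: 7.5 / 5 = 1.50
- f = 0.10: 7.75 / 5.5 = 1.41
- f = 0.25: 8.125 / 6.25 = 1.30
- f = 1: 10 / 10 = 1.00, which is the protocol wording

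This assumes that counted reductions are half as common on obicetrapib. If at f = 0.25 they are equally common in both arms (1.25% each), the ratio is (7.5 + 1.25) / (5 + 1.25) = 8.75 / 6.25 = 1.40. If they rise in step with hypertension AEs (1.25% × 1.5 = 1.875%), it is 9.375 / 6.25 = 1.50, with no dilution.

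**The case against.** The strongest reply is that SAP 3.5.2 is the only operational derivation and already carries most of the direction needed. Nothing counts in the treated stratum without a hypertension-related AE, a dose cut for low pressure without one drops out, and the untreated stratum counts initiation only. This stands, and it limits the point to dilution. A reader might infer from the protocol wording that a pressor effect would vanish from the planned final table. The SAP rule does not support that unless nearly all reductions fall near a hypertension AE.

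A reader might also infer that the DSMB will see a pooled, insensitive count. The documents do not show this. Protocol 9.2.5 and SAP Section 4 refer the details to a charter that is not available here. Protocol 8.2.5 says only "These ESIs will be monitored through review of the AE and laboratory databases", and Protocol 8.9.1 has the DSMB review systolic and diastolic readings over time. Any effect on its reviews is conditional on the charter.

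Third, a two-sided definition may have been intended, since Protocol 8.2.5.5 speaks of changes in pressure generally. That may be so, but it is a reason to show both directions, not to merge them.

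Finally, SAP 3.5 rules out inference on safety endpoints, SAP 3.5.2 lists each ESI, SAP 3.5.4 counts office readings above set thresholds, and SAP 3.5.7 tests ambulatory systolic pressure against a 3 mmHg margin. These measures are directional and justify a low rating. They do not remove the defect: a listing is not a between-arm count, and the ambulatory data cover about 200 participants with one post-Baseline assessment.

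**Conclusion.** The point holds as a minor one. The protocol definition is undirected. The SAP corrects most of that, but in the Baseline-treated stratum a reduction, or a stop that preceded the AE, is still scored as due to a blood pressure change, and six direction-neutral terms can trigger the rule.

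Under the SAP rule the illustration gives a ratio of 1.30 to 1.50 against a true 1.50 if at most 25% of reductions fall near a hypertension AE. A ratio of 1.00 arises only under the undirected protocol wording with the rates assumed. Every rate is an assumption. The range also depends on whether reductions near a hypertension AE become rarer, stay level or become more common on the drug, which the documents do not address. Because no test is planned on this ESI, the ratios describe how visible a difference would be, not the loss of a formal comparison.

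**What to change.** In SAP 3.5.2, for the Baseline-treated stratum:

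1. Classify each counted change as (a) start, addition or dose increase, or (b) stop or dose decrease. Tabulate (a) and (b) by arm in separate rows, with switches between drugs in their own row.
2. Within (a), make changes starting on the AE start date or up to 30 days after it the main count. Put changes dated before the AE in a separate row and do not discard them. SAP 3.1.8 sets an incomplete start date to the first of the month, so a drug truly started after a mid-month AE could be dated before it and lost under a strict forward window.
3. Show the count with and without the six direction-neutral Appendix B terms.
4. Align Protocol 8.2.5 and 9.2.2.1 with SAP 3.5.2, including the extension to participants untreated at Baseline.

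Row (b) should be labelled as reductions near a hypertension-term AE, not as reductions for low pressure: Appendix B has no hypotension terms, so the latter cannot be derived from it.

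The cost is a few lines of programming, some extra table rows and fewer events per row. Medication start and stop dates are recorded (SAP 3.3.6). Classifying dose changes depends on antihypertensive doses being recorded, which the documents do not expressly confirm. If they are not, starts and stops can still be separated by date. No visit or clinical rule changes.
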